6.4.4 Rewet Procedure Measurement

After the participants have been dismissed from the study, the Medline Industries, LP. statistical team will calculate the rewet testing results using the weights collected during the rewet testing. The rewet measurement will be calculated as follows:

Rewet measurement = (weight of the wetted filter paper) - (weight of the dry filter paper)

6.4.5. FitRight® Pod Disinfection

The FitRight® Pods should be disinfected between participants. To disinfect the FitRight® Pods, study staff will don gloves and wipe all surfaces of the FitRight® Pod with EPA- registered 0.65% bleach concentration solution and allow for proper dry time. After disinfecting, study staff will remove and dispose of gloves and perform optimal hand hygiene. Study staff will record the number of times that the pod has been disinfected. Each pod has a maximum of 12 disinfections. Once a FitRight® Pod has been disinfected 12 times, the pod can no longer be used and will be returned to Medline Industries, LP.

7 ADVERSE DEVICE EVENTS (ADEs)

7.1 Definition of Adverse Device Event (ADE)

Any adverse event related to the use of an investigational medical device resulting from insufficiencies or inadequacies in the instructions for use, the deployment, installation, the operation, or any malfunction of the investigational medical device or from error use.

7.2 Definition of Serious Adverse Device Event (SADE)

Any adverse device events that have resulted in any of the consequences characteristic of a serious adverse event. The FDA definition of a SAE will be used in this study: An AE or suspected adverse reaction is considered "serious" if, in the view of either the PI or sponsor, it results in any of the following outcomes:

- Death,
- A life-threatening adverse event,
- Inpatient hospitalization or prolongation of existing hospitalization,
- A persistent or significant incapacity or substantial disruption of the ability to conduct normal life functions, or
- A congenital anomaly/birth defect.

Important medical events that may not result in death, be life-threatening, or require hospitalization may be considered serious when, based upon appropriate medical judgment, they may jeopardize the participant and may require medical or surgical intervention to prevent one of the outcomes listed in this definition. All SADEs will be reported to Medline, regardless of potential relationship to the study product(s). SADEs will be reported to the reviewing IRB as necessary according to their reporting requirements.

7.3 Definition of Unanticipated Adverse Device Effect (UADE)

Any serious adverse effect on health or safety or any life-threatening problem or death caused by, or associated with, a device, if that effect, problem, or death was not previously identified in nature, severity, or degree of incidence in the investigational plan or application (including a supplementary plan or application), or any other unanticipated serious problem associated with a device that relates to the rights, safety, or welfare of participants.

7.4 Severity of Adverse Device Event

The severity of all AEs will be graded on a scale of one through five according to the Common Terminology Criteria for AE guideline, where each grade represents a unique clinical description based on this general guideline:

- **Mild (1 = Grade 1):** Awareness of signs or symptoms, but easily tolerated; are of minor irritant type, causing no loss of time from normal activities; symptoms would not require medication or a medical evaluation; signs and symptoms are transient.
- **Moderate (2 = Grade 2):** Discomfort severe enough to cause interference with usual activities; requiring treatment but not extended hospitalization or intensive care for the participant.
- **Severe (3 = Grade 3):** Incapacitating with inability to do work or usual activities; signs and symptoms may be systemic in nature or require medical evaluation and/or treatment; requiring additional hospitalization or intensive care (prolonged hospitalization).
- **Life-threatening (4 = Grade 4):** At immediate risk of death in view of the investigator, or it is suspected that the use or continued use of the product would result in participant's death; urgent intervention indicated.
- **Death (5 = Grade 5):** Death related to adverse event.

7.5 Relatedness of Adverse Device Event and Serious Adverse Device Event

List the criteria for determining the probability that a given AE is related to participation in the study. A common rating system is provided below.

- **Unrelated:** This category applies to those AEs which, after careful consideration, are clearly and incontrovertibly due to extraneous causes (disease, environment, etc.)
- **Possible:** This category applies to those AEs for which, after careful medical consideration at the time they are evaluated, a connection with the Investigational Product administration appears unlikely but cannot be ruled out with certainty.
- **Probable:** This category applies to those AEs which, after careful medical consideration at the time they are evaluated, are felt with a high degree of certainty to be related to the study product(s).
- **Definite:** This category applies to those AEs which, after careful consideration, are clearly and incontrovertibly due to the study product(s).

7.6 Expectedness

The site PI will be responsible for determining whether an ADE or SADE is expected or unexpected. An AE will be considered unexpected if the nature, severity, or frequency of the event is not consistent with the risk information previously described.

Expected ADEs or SADEs may include any ADEs or SADEs that may occur as a result of using the FitRight Wetness Sensing System including but not limited to the following:

- **Skin irritation** or inflammation causing pain, discomfort and swelling.
- **Contact dermatitis:** Skin AEs potentially related to the brief and securement including itching, rash, blister, skin tear, bruising, and pressure areas

The PI will be responsible for determining whether an ADE or SADE is anticipated or unanticipated. An AE will be considered unanticipated if the nature, severity, or frequency of the event is not consistent with the risk information previously described for the study intervention.

7.7 Adverse Device Event (ADE) Reporting

The ADEs will be recorded on the ADE Form (provided by Medline Industries, LP.) by the study staff and reviewed by the PI. Changes in the severity of an ADE will be documented to allow an assessment of the duration of the event at each level of severity. Changes in severity will necessitate a new ADE Form to document the new level of severity. ADEs characterized as intermittent require documentation of onset and duration of each episode.

Non-serious ADEs will be reported to the study sponsor on a monthly basis for review or as agreed upon with the study sponsor and reported to the IRB per IRB reporting requirements.

7.8 Serious Adverse Device Event and Unanticipated Adverse Device Effect Reporting

The PI shall complete an SADE Form (provided by Medline Industries, LP.) and submit to the study sponsor as soon as possible, but in no event later than 48 hours after the PI first learns of the effect. The PI will be responsible for reporting the event to the IRB, if applicable, per the IRB's reporting requirements. The study sponsor is responsible for conducting an evaluation of the SADE and shall report the results of such evaluation to the FDA and to all reviewing IRBs, if applicable, within 10 working days after the sponsor first receives notice of the effect. Thereafter, the sponsor shall submit such additional reports concerning the effect as FDA requests.

For questions regarding this process or the event, you may contact your Medline clinical designee or the Medline Director of Clinical Operations.

Name: [name] BSN CCRA
[contact]
E-mail: [contact]

8 STATISTICAL CONSIDERATIONS

8.1 Sample Size Determination

A sample size of 56 was chosen to evaluate the 95% confidence interval on the proportion of successful wetness alerts. The NCSS PASS procedure "Confidence Intervals for One Proportion" was used to solve for "CI width or distance from P to limit". It was assumed that the proportion of successes would be around 90% (0.85, 0.90 and 0.95 entered into PASS). Because testing will occur in 8 subgroups, the largest sample size that was a multiple of 8 that provided the most narrow 95% confidence limits was selected (N=56).

Rewet testing sample size: A convenient subset of the first 22 completed patients will be recruited for the rewet procedure. Patients will be considered complete if they have all data, for all three of the brief tests.

8.2 Randomization

Patients were randomized into two equal groups of 28 by means of a SAS® software generated random seed number and randomization program (Copyright © 2013 SAS Institute Inc.) only for the side position. Twenty-eight patients will complete the test using their right side and 28 will complete the test using their left side. Practically, it will be impossible to blind the staff and patients to the left or right side, as it will be apparent. Thus, the randomization will only be blinded to the analyst to ensure an un bias analysis.

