1.2 Schedule of Activities (SOA)

Study Timeline of Events ^a	Pre-Study	During the Study	End of the Study
Informed Consent	X		
Verification of eligibility	X		
Randomization	X		
Participant applies first brief with tubing (study staff checks for correct application) and participant sits in sitting position.		X	
Study staff pours 90mL saline and starts timer for five minutes.		X	
After five minutes, staff records whether an alert was triggered. Staff pours an additional 150mL saline and starts a timer for five minutes. ^{b, c}		X	
After five minutes, staff records whether an alert was triggered. Staff pours an additional 120mL saline and starts a timer for five minutes. ^{b, c}		X	
After five minutes, staff records whether an alert was triggered. Staff pours an additional 120mL saline and starts a timer for five minutes. ^{b, c}		X	
After five minutes, staff records whether an alert was triggered. ^d		X	

Participant removes the first brief and applies second brief with new tubing (study staff checks for correct application) and participant lays in supine position.		X	
Study staff pours 90mL saline and starts timer for five minutes.		X	
After five minutes, staff records whether an alert was triggered. Staff pours an additional 150mL saline and starts a timer for five minutes. ^{b, c}		X	
After five minutes, staff records whether an alert was triggered. Staff pours an additional 120mL saline and starts a timer for five minutes. ^{b, c}		X	
After five minutes, staff records whether an alert was triggered. Staff pours an additional 120mL saline and starts a timer for five minutes. ^{b, c}		X	
After five minutes, staff records whether an alert was triggered. ^d		X	
Participant removes the second brief and applies third brief with new tubing (study staff checks for correct application) and participant lays in their randomized side position (either left or right side).		X	
Study staff pours 90mL saline and starts timer for five minutes.		X	
After five minutes, staff records whether an alert was triggered. Staff pours an additional 150mL saline and starts a timer for five minutes. ^{b, c}		X	
After five minutes, staff records whether an alert was triggered. Staff pours an additional 120mL saline and starts a timer for five minutes. ^{b, c}		X	
After five minutes, staff records whether an alert was triggered. Staff pours an additional 120mL saline and starts a timer for five minutes. ^{b, c}		X	

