6.4.1. Application of the FitRight Wetness Sensing System

Participants will be measured for their hip circumference. Participants will be given the brief for their size (available sizes are medium-2XL) that corresponds to the circumference measurement. Study staff will use their discretion to select the applicable size. Study staff will record on the CRF which size was provided to the participant. Following the IFU, participants will be given space to privately apply the FitRight® Brief and tubing. Once the brief is on and tubing is in place, study staff will apply exam gloves and assess the brief for correct application. If the brief or tubing needs to be adjusted, participants will be given more time to privately make adjustments. The tubing should be placed directly in the center of the bottom of the brief at the approximate location of urination.

Once the tubing is in place and the brief is applied correctly, participants will be instructed to sit on the bed in a sitting position. If the tubing moves, participants should again adjust the tubing to the correct position. Study staff will then apply the FitRight® Pod to the brief according to the IFU and make sure that the FitRight® App is indicating the Pod is connected. Once the FitRight® Pod and FitRight® App are properly setup, study staff will connect the tubing in the brief to the tubing connected to the funnel system.

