Participants will remove the brief and apply a new brief (in their appropriate size) with new tubing as outlined in Section 6.4.1. Participants will be asked to lay in a supine position and study staff will perform the same steps as outlined in Section 6.4.2 above. Once participants and study staff have completed all steps in the supine position, participants will remove the brief and apply another new brief (in their appropriate size) with new tubing as outlined in Section 6.4.1. Study staff will refer to the Randomization Schedule to determine the next position the participant will be in (laying on either the left or right side). Study staff will then perform all of the same steps as outlined in Section 6.4.2.

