8.9.1 Analysis of Primary Endpoints

The primary goal of this research study is to assess the reliability of the FitRight® Alert Indicator for the full sample and stratified by the four rotational positions, the three different fluid amounts,

and the combination of rotational positions and fluid amounts. Cronbach's coefficient alpha estimate's reliability by determining the internal consistency of a test or the average correlation of items within a test. The pass/fail values from this set of test runs will be compared to the derived variable of whether or not the test should have triggered an alert. Since the variables of interest are dichotomous (pass/fail), the coefficient alpha is equivalent to the Kuder-Richardson 20 (KR-20) reliability measure. It produces a correlation measure between 0 where a high KR20 coefficient (e.g., >0.90) is indicative of a homogeneous test. A reliability of 0.70 or higher for an acceptable rating and 0.80 or higher for a good rating.

In addition, a chi-square analysis will be conducted to determine if any association between rotational position and test status (pass/fail) exists. This analysis will be repeated to examine any possible associations between fluid added and test status (pass/fail).

Spearman correlation analysis will be used to examine possible associations between the key variables of triggered alert value (pass/fail), rotational position (sitting, supine, left side, right side), and fluid volume of 90 mL, 150 mL, 120 mL, and 120 mL with covariates of age, sex, and brief size. Additional t-tests or non-parametric tests will be employed to further examine any significant associations found in the correlational analyses between key and covariate measures.

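### The fixed test order (sitting, supine, side) cannot be separated from position in the planned chi-square; left versus right is not affected

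*Combined protocol and SAP*

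**What the plan says.** The order is the same for everyone, and several sections agree on it.

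- Section 1.2 starts with the first brief in the sitting position. It continues "Participant removes the first brief and applies second brief with new tubing" for supine, and then "Participant removes the second brief and applies third brief with new tubing" for the side position.
- Section 6.4.1 gives the first position: "participants will be instructed to sit on the bed in a sitting position". Section 6.4.2 gives the second: "Participants will be asked to lay in a supine position and study staff will perform the same steps as outlined in Section 6.4.2 above". Only after that does the participant move to the side position, where the Randomization Schedule is consulted for left or right.
- Section 8.2 limits randomisation: it applies "only for the side position". The split is equal: "Twenty-eight patients will complete the test using their right side and 28 will complete the test using their left side".
- Section 8.9.1 adds to the reliability analysis that "a chi-square analysis will be conducted to determine if any association between rotational position and test status (pass/fail) exists". Section 8.9 sets the threshold at 0.05.
- Section 8.6 codes position in four levels (sitting, supine, left, right). It lists no variable for brief order, and 8.9.1 contains none.
- Section 6.4.5 says "The FitRight® Pods should be disinfected between participants". No section says whether the Pod is changed between briefs.

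The synopsis and section 5.4 list supine first in places, but those lists only name the positions and set no different sequence.

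**The concern.** Position is named in the primary objective, and the plan intends a significance test across positions. With a fixed sequence, a difference between sitting and supine is also a difference between the first and second brief, and side against either is also third brief against first or second.

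There are possible routes for an order effect. Participants fit the brief and tubing themselves and repeat this within a visit. An earlier brief may have taken up to 90 + 150 + 120 + 120 = 480 mL, and no skin-drying step is written between briefs. The same Pod may stay in use.

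At stake is the reading of that one comparison. An order effect could be reported as a position effect. A gain with practice could also hide poorer sensing in the later positions.

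**Working it through.** **Plan's own figure.** The plan gives none for the position comparison. Section 8.1 sizes the study for a 95% confidence interval on one proportion and states no width. At p = 0.90 and n = 56 the full Wald width is 2 × 1.96 × √(0.90 × 0.10 / 56) = 0.157. That interval needs no position contrast, and this point does not depend on it.

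**Inputs.** 56 participants with three tests each, so 168 tests (8.1, 1.2); order fixed (1.2, 6.4.1, 6.4.2); 28 left and 28 right (8.2); four position levels (8.6); threshold 0.05 (8.9); pass rate around 0.90, with 0.85 and 0.95 also entered (8.1). The size of any order effect is not given, so the values below are assumptions.

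**Step 1: what the contrast estimates.** Write the expected pass rate as position effect plus brief-order effect. Under the fixed order:

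- supine − sitting = (position supine − position sitting) + (brief 2 − brief 1)
- side − supine = (position side − position supine) + (brief 3 − brief 2)
- left − right = (position left − position right) + (brief 3 − brief 3), so order cancels

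For example, a true supine deficit of 0.05 together with a practice gain of 0.05 from brief 1 to brief 2 gives an expected difference of zero.

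**Step 2: estimability.** Take a linear model with six columns: intercept, supine, left, right, brief 2, brief 3. Under the fixed order the supine column equals the brief 2 column, and left + right equals brief 3. Those two dependencies leave rank 6 − 2 = 4. Checked numerically on 168 rows:

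| Contrast | Fixed order (rank 4 of 6) | Six orders counterbalanced (rank 6 of 6) |
|---|---|---|
| supine vs sitting | not estimable | estimable |
| left vs sitting | not estimable | estimable |
| right vs supine | not estimable | estimable |
| left vs right | estimable | estimable |

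**Step 3: how much it could matter.** The planned four-level chi-square (3 df, 0.05) was simulated in 20,000 trials per row. There was no true position effect, pass rates depended only on brief number, and tests were taken as independent.

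| Assumed pass rate, briefs 1/2/3 | Rejects, fixed order | Rejects, counterbalanced |
|---|---|---|
| 0.90 / 0.90 / 0.90 | about 5% | about 5% |
| 0.95 / 0.90 / 0.85 | about 30% | about 4% |
| 0.90 / 0.85 / 0.80 | about 22% | about 5% |
| 0.85 / 0.90 / 0.95 | about 22% | about 4% |
| 0.95 / 0.85 / 0.75 | about 75% | about 4% |

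**Step 4: balance at N = 56.** 56 / 6 = 9.33 per order and 28 / 6 = 4.67 per order within each side. Each side therefore holds four complete blocks of six (24 participants) plus four more, so each order occurs four or five times per side. If the two orders left out of the last block differ between left and right, four orders occur 9 times and two occur 10 times: 4 × 9 + 2 × 10 = 56.

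**The case against.** The strongest case against has three parts.

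First, scope. The study is sized for one proportion, its key outputs are pass percentages overall and by position, the chi-square is an addition, and no success criterion hangs on it. This stands. A reader might infer that the trial cannot say whether the sensor works in each position, or that every position result is confounded. The documents do not support that. Per-position rates need no contrast, and left versus right is randomised with both sides tested in brief 3.

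Second, plausibility. Each position has a new brief and new tubing, staff check the fit each time, staff are trained beforehand, and the sensing ink is on the backsheet of the brief that is replaced. Nothing says the Pod changes over three consecutive uses. This also stands as far as it goes. A reader might infer that an order effect is present, but the documents give no evidence of one and no size. These safeguards make a large effect less likely. They do not make the contrast identifiable, because the aliasing holds whatever the size.

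Third, practicality. A three-sequence Latin square would leave each position always preceded by the same other position, so carry-over would not be balanced. A plain chi-square cannot hold an order term. Section 8.2 is partly in the past tense, so the list may already exist. These objections shape the fix rather than defeat the point.

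**Conclusion.** The point holds for sitting versus supine versus side, and only there. All 56 participants follow one sequence, so the aliasing is complete and follows from the design alone, with no numerical assumption. It cannot be repaired at analysis.

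The practical size is unknown. The rejection rates of about 22% to 75% rest on assumed shifts of 5 or 10 percentage points per brief and on independent tests. With no order effect the test rejects at about its nominal 5%.

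This should be changed, because the plan attaches a significance test to a comparison its design cannot attribute to position. It does not undermine the overall pass rate, the per-position rates read as results of this sequence, or the left versus right comparison.

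**What to change.** **If testing has not begun.** Extend the 8.2 schedule so that it assigns the order of the three positions as well as the side. Use all six orders in permuted blocks of six, stratified by the left/right assignment. Balance at N = 56 is near rather than exact, about 9 to 10 per order. Any rewet brief stays last. Reword 1.2, 6.4.1 and 6.4.2 so that they no longer fix the sequence, and add brief order (1, 2, 3) to the variables in 8.6.

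In 8.9.1, replace the position chi-square with a within-participant model for pass/fail, for example logistic GEE clustered by participant, with position and brief order as factors. This also accounts for three tests coming from the same person, which the chi-square ignores. Failures will be few: at a 0.90 pass rate, 168 × 0.10 = 16.8 in all, of which 28 × 0.10 = 2.8 are expected on each side. The plan should therefore state in advance what is done if a position has no failures.

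**If testing has begun.** Keep the order, report the sitting/supine/side comparison as descriptive only, and state in 8.9.1 that it is confounded with test order. Left versus right can still be tested.

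**Cost.** A new randomisation list, an order card for staff, a changed CRF page order and a revised analysis paragraph. No extra participants or briefs are needed. The second option costs one or two sentences.
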